Official Title:	Clinical Trial Tobacco Marijuana
NCT number:	02277665
Document Type:	Cover Letter and Protocol
Date of the Document:	August 1, 2018

Study Protocol and Analysis Plan

2.1 Participants. Participants seeking treatment for CUD were enrolled between October 2014 to September 2016 at Dartmouth College and the University of Washington. The study was conducted in compliance with Internal Review Boards at Dartmouth College and the University of Washington and registered on clinicaltrials.gov (NCT02277665). Participants at both sites were recruited from advertisements posted online (Craigslist, Facebook), in newspapers, on radio, posters throughout the community, and notices to professionals and service agencies. Participants were included if they met the following criteria: 1) ≥ 18 years of age, 2) current diagnosis of cannabis abuse or dependence made using the Structured Clinical Interview for DSM-IV (SCID: First et al., 1995), 3) cannabis use on ≥ 45 of the past 90 days, 4) regular use of tobacco (i.e. ≥ 5 days per week) or report primary administration of cannabis via blunts/spliffs, and 5) self-reported at least minimal interest in quitting tobacco in the next six months during the pre-intake screening (i.e. rating of ≥ 2 on a 5-point scale). Exclusion criteria included: 1) current dependence (DSM-IV criteria) in the last 6 months on alcohol or any drug other than tobacco and cannabis with the exception of opiate dependence maintained with agonist replacement therapy, 2) use of non-tobacco nicotine (i.e. nicotine replacement therapy, NRT), or exclusive use of smokeless tobacco products, 3) currently in treatment for substance dependence, 4) severe psychological distress (e.g. active suicidal ideation, debilitating panic disorder), 5) medical condition that required physician approval before using NRT (e.g. pregnancy or myocardial infarction), 6) legal status that would interfere with participation, 7) living with someone enrolled in the study, 8) not fluent in English, or 9) living ≥ 45 miles from the study site.

Of the 146 participants screened for the study, 53 did not meet inclusion / exclusion criteria, 15 were eligible but declined treatment, and 11 did not enroll for other reasons (e.g. lost contact after intake) (see Figure 1). Sixty-seven adults (45 male), age 18-60 years signed a study consent and were enrolled. Participant characteristics by treatment condition are presented in Table 1.

2.2 Interventions

2.2.1 CUD Intervention. The CUD treatment approach has been described previously (Budney et al., 2011, 2015; Lee et al., 2014, 2015). Briefly, this treatment comprised a 9-session computer-assisted delivery of a motivational enhancement therapy (MET), cognitive behavioral therapy (CBT) and abstinence-based contingency management (CM) provided over 12 weeks. Participants attended the clinic twice weekly, where they received nine MET/CBT computer modules (weeks 1-8 and week 12), three 15 to 30-minute supportive counseling sessions (weeks 1, 4 and 12), and provided urine specimens. Computer modules were also available remotely with individualized passwords throughout the study. The CM program targeted cannabis abstinence by providing an escalating schedule of monetary incentives contingent on cannabis-negative urine toxicology derived from twice-weekly observed urine specimens. Participants could earn up to \$435 for continuous abstinence throughout the intervention. Incentives were delivered after each visit via electronic deposits to a debit card.

2.2.2. Tobacco Intervention (TI). The TI included NRT and seven computer-delivered psychoeducational and behavioral counseling modules developed specifically for this project.

The first module was a translated and adapted version of a Swiss/French language, evidence-based, on-line assessment and feedback program (Stop Tabac: Etter, 2005, 2009; <http://www.stop-tobacco.ch/en/>), which focused on the pros and cons of smoking tobacco, encouraged motivated participants to set a tobacco quit date, and included a personalized tobacco use feedback report. The second module provided information about co-use of cannabis and tobacco, including potential additive health risks, difficulties with quitting one substance while continuing to smoke the other, planning to quit both substances, and roadblocks to quitting both. The third module provided NRT education and instruction. The fourth module focused on planning for change and setting a quit date. The fifth module provided reduction strategies for those interested in reducing rather than quitting. The sixth module included information and strategies for relapse prevention. The seventh module provided education on electronic cigarettes. The TI modules could be accessed remotely at any time with individualized passwords.

At each visit, participants were encouraged by staff, but not required, to complete at least one module and consider initiation of NRT. Participants were required to complete the NRT education module prior to receiving NRT. NRT was provided on a bi-weekly schedule free of charge and could be initiated anytime during the TI. NRT options included a combination of patch and gum or lozenges, following standard guidelines for dosing (Stead et al., 2012).

2.3 Trial Design, Treatment Conditions, Hypotheses

This two group, 24-week study randomized participants seeking treatment for CUD to either a simultaneous (SIM) or a sequential (SEQ) treatment condition (Figure 1). Urn randomization procedures balanced the conditions on the following baseline characteristics: cannabis abstinence prior to treatment initiation, tobacco dependence severity (low vs. high, based on the Fagerstrom), blunt/spliff smoker or not, ethnicity (African American or not), and gender. Assessments occurred at week 12 (end of Phase 1) and week 24 (end of Phase 2).

2.3.1. SIM Condition. During weeks 1-12 (Phase 1), participants in the SIM condition received immediate access to the previously described CUD and tobacco interventions. The first five CUD MET/CBT modules were completed in a fixed order starting at the first visit. The TI modules and NRT were also available starting at the first visit, but for most participants, this did not occur until the second visit due to time constraints. TI modules could be completed in any order selected by participants, but as per above, NRT was not available until the NRT education module was completed. Both the CUD and TI modules viewed during clinic visits could then be accessed remotely with an ID and password. During weeks 13-24 (Phase 2) SIM participants could continue to access the cannabis and tobacco intervention modules ad libitum remotely but did not attend clinic visits or receive additional NRT. SIM participants that expressed an interest in continuing NRT after Phase 1 were provided with a one-week supply and instructed on how to purchase additional NRT on their own. For those not interested in continuing use, NRT dose was tapered during weeks 10-12 to reduce the probability of nicotine withdrawal symptoms from discontinuation.

2.3.2 SEQ Condition. During Phase 1, SEQ participants received only the CUD MET/CBT/CM intervention. They could not access the TI modules, NRT was not provided by the clinic, and no counseling for tobacco cessation was offered. During their first visit, they were given a booklet on tobacco cessation, *Clearing the Air*

(<https://www.cancer.gov/publications/patient-education/clearing-the-air>) that provided education and guidelines for quitting and a Quitline telephone number (SIM participants also received the booklet). This reflected “treatment as usual” for tobacco cessation in the context of outpatient treatment for CUD. SEQ participants interested in tobacco cessation during Phase 1 could make cessation attempts but had to obtain tobacco medications on their own. During Weeks 13-24, (Phase 2), SEQ participants were offered the TI as described above, and encouraged to attend weekly clinic visits to help facilitate engagement and adherence. Note that during Phase 2 clinic staff were highly flexible and encouraging of any attendance schedule with the primary goal of accommodating participants so that they could complete TI modules and obtain NRT.

2.3.3 Primary Hypotheses. Based on prior pilot study and the literature on targeting tobacco use in the context of treatment for other SUDs, we hypothesized that: (1) the TI would be acceptable to participants in the SIM condition (i.e., Phase 1 retention and CUD engagement would not differ between conditions, and that the majority of SIM participants would engage with the TI components; (2) during Phase 1, the SIM condition would engender greater use of NRT, more tobacco quit attempts, greater sustained tobacco abstinence than SEQ, and cannabis abstinence would not differ between conditions; (3) at the end of Phase 2, after participants in both conditions were exposed to the TI, a greater percentage of SIM than SEQ participants would have initiated NRT and made a tobacco quit attempt.

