made at least one self-reported tobacco quit attempt during Phase 1, and percent of participants who achieved sustained tobacco abstinence over the final eight weeks of Phase 1. Secondary outcomes included: percent of participants who achieved any biologically-verified cannabis or tobacco abstinence (≥ 1 negative urine THC/cotinine specimen or expired carbon monoxide < 5 ppm), percent of participants who achieved cannabis abstinence throughout the final four weeks of treatment, reduction in percent days of cannabis and tobacco use during treatment relative to baseline, and point-prevalence cannabis and tobacco abstinence at the 12-week follow-up assessment.

2.6 Data Analysis. Sociodemographic and baseline drug use characteristics between treatment conditions were compared using t-tests for continuous measures and chi-square tests for nominal measures (Table 1). The primary cannabis and tobacco abstinence outcomes were analyzed using an intent-to-treat approach with missing biological verification data and dropouts treated as a positive indicator of cannabis or tobacco use. Longest duration of continuous abstinence from cannabis (primary), number of days abstinent from tobacco, and number of tobacco quit attempts (primary) were all zero-inflated and therefore could not be analyzed with models that assume continuous, normally distributed outcomes. We therefore analyzed each of these outcomes using a zero-inflated Poisson model which provides an odds ratio describing the relative likelihood of achieving a zero-response to the outcome in the two treatment arms and a ratio of means describing the relative mean of the outcome in the two treatment groups. Additionally, several binary outcomes were analyzed via chi-square tests: cannabis abstinence in the final 4 weeks, point prevalence abstinence at the end of treatment, achievement of at least 50% reduction in days of using cannabis from intake to the final 4 weeks, and achievement of continuous tobacco abstinence for ≥ 2 consecutive weeks. Phase 2 outcomes were analyzed using descriptive statistics. Statistical comparisons were not made between SEQ Phase 2 and SIM Phase 1 outcomes because of the lack of Phase 2 data due to only a 30% participation rate for SEQ during Phase 2. All analyses were performed using SAS version 9.4.

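### Site is not a listed urn factor and does not enter the Section 2.6 analysis of this 67-person, two-site trial; the comparison is valid on average, but a site-stratified analysis would protect the one realised trial at almost no cost

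*Combined protocol and SAP*

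**What the plan says.** Section 2.1 describes participants "enrolled between October 2014 to September 2016 at Dartmouth College and the University of Washington" and gives the total: "Sixty-seven adults (45 male), age 18-60 years signed a study consent and were enrolled". Enrolment per site is not given.

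Section 2.3 describes allocation: "Urn randomization procedures balanced the conditions on the following baseline characteristics: cannabis abstinence prior to treatment initiation, tobacco dependence severity". Severity is dichotomised on the Fagerstrom score. The remaining factors are blunt or spliff smoking, ethnicity (two categories) and gender, which makes five in all. Nothing says whether one urn served both institutions or each ran its own.

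Section 2.6 gives the analysis. Duration of continuous cannabis abstinence, days abstinent from tobacco and number of tobacco quit attempts go into zero-inflated Poisson models that contrast the two arms. In addition, "several binary outcomes were analyzed via chi-square tests": cannabis abstinence in the final four weeks, end-of-treatment point prevalence, a halving of cannabis use days, and at least two weeks of continuous tobacco abstinence. No covariate, stratum or site term is named. For attendance, module completion and NRT initiation, which Section 2.5 lists as primary engagement outcomes, Section 2.6 names no test.

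**The concern.** Two clinics can differ in the people they recruit and in how well those people attend, abstain and attempt to quit. If the arms also differ in their mix of clinics, part of that difference appears in the SIM-SEQ contrast, and an analysis without site cannot separate the two.

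The contrasts most exposed are those for which Section 2.3.3 predicts no difference: Phase 1 retention, engagement with the cannabis treatment, and cannabis abstinence. No margin is given for any of them, so a shift of a few points could hide a small deficit or create the look of one.

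There is a second route. If allocation was in fact balanced within site, ignoring site leaves between-site variation in the standard error, and the tests lose some power. In either case the document does not let a reader tell which situation applies.

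**Working it through.** **Reproducing the stated figure.** The only total that can be checked is enrolment: 146 screened − 53 not eligible − 15 declined − 11 other reasons = 67. It matches. The document gives no sample-size or power calculation.

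**Inputs.** From the document: 67 participants, two sites, two arms, site not listed as an urn factor. Assumed, because not given: arms of 34 and 33; one site contributing 20, 27, 34 or 40 of the 67; allocation unrelated to site; a difference in response between sites of 20 to 30 points (10 to 40 in the wider range); 40% mean response; two-sided 5% level.

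**Step 1: size of a chance imbalance.** Let m be the size of site A and X the number of its participants in the arm of 34. X is hypergeometric (67, m, 34), and the difference in site share is D = X/34 − (m − X)/33.
- For m = 34: Var(X) = 34 × (34/67) × (33/67) × (33/66) = 4.25, so SD(X) = 2.06. Then SD(D) = 2.06 × (1/34 + 1/33) = 2.06 × 0.0597 = 0.123.
- For m = 20: SD(D) = 0.113.

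| Site A size | Mean abs. D | SD of D | P(abs. D ≥ 10 pts) | ≥ 15 pts | ≥ 20 pts |
|---|---|---|---|---|---|
| 20 | 9.0 pts | 11.3 pts | 42.5% | 18.3% | 6.1% |
| 27 or 40 | 9.7 pts | 12.1 pts | 46.0% | 21.8% | 8.4% |
| 34 | 9.9 pts | 12.3 pts | 46.7% | 22.5% | 8.9% |

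**Step 2: shift in the arm contrast.** Shift = D × site difference in outcome.
- Typical (mean absolute) imbalance: from 0.090 × 20 = 1.8 points to 0.099 × 30 = 3.0 points, so about 2 to 3 points.
- A 20-point imbalance: 0.20 × 20 = 4 points to 0.20 × 30 = 6 points. Site differences of 10 and 40 points would give 2 and 8 points.

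**Step 3: compare with sampling error.** At 40% response, SE = √[0.4 × 0.6 × (1/34 + 1/33)] = √0.01433 = 0.120, or 12 points. The typical shift is 1.8/12 to 3.0/12, about 0.15 to 0.25 of a standard error. The 20-point case is 4/12 to 6/12, or one third to one half.

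**Step 4: effect on the test.** In 200,000 simulated trials per setting with no treatment effect (sites of 34 and 33), the rejection rates were:

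| Site difference | Chi-square, all trials | Chi-square, imbalance ≥ 20 pts | CMH by site, imbalance ≥ 20 pts | Chi-square, balanced within site | CMH, balanced within site |
|---|---|---|---|---|---|
| 20 pts | 4.8% | 6.7% | 5.1% | 4.3% | 4.8% |
| 30 pts | 4.8% | 8.2% | 4.5% | 3.8% | 4.8% |
| 40 pts | 4.8% | 11.8% | 4.9% | 3.1% | 5.0% |

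The unadjusted test holds its level over all randomisations. It departs from that level only when one looks within badly imbalanced allocations, and it is conservative when sites are balanced by design. The stratified test stays near 5% throughout.

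**The case against.** The strongest case against is that nothing is known to have gone wrong. Randomisation leaves the unadjusted contrast unbiased on average. A shift needs both an imbalance and an outcome difference between sites, and the document reports neither. The 20 to 30 point site difference is an assumption. The raised rejection rates apply only to the fewer than 9% of allocations with an imbalance of at least 20 points. The typical shift is small beside the standard error. Separate urns per site are not excluded, and Table 1 and Figure 1, which are not shown in the text available, may report site. All of this stands, and it limits the size of the point. It does not remove it, because the stratified test does at least as well on level in the settings that matter and the allocation procedure is left unstated.

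A reader might also infer that site matters especially here because uptake rests on local staff: "At each visit, participants were encouraged by staff, but not required, to complete at least one module and consider initiation of NRT". The document does not support that for the arm contrast. The sentence describes the tobacco intervention, and SEQ had no access to its modules and no clinic-supplied NRT in Phase 1. Site mix cannot create or hide an arm difference in tobacco module completion that is absent from SEQ by design. The flexible attendance described in Section 2.3.2 belongs to SEQ in Phase 2, which is analysed descriptively. Section 2.4.1 mentions excused absences but does not say who grants them, so local discretion is only an inference.

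Finally, stratifying the tests named in Section 2.6 would not by itself reach attendance or module completion, since no test is named for them. The fix has to cover these separately.

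**Conclusion.** The point holds in a limited form. Site is absent from the listed urn factors and from the analysis, and the document does not say whether urns were site-specific. The reported comparison is not invalid, and the text gives no ground for saying that the results are biased. What is lost is protection of the single realised trial: on the assumptions listed above, a typical shift of 2 to 3 points and, in the less likely allocations, 4 to 6 points or more, against a standard error of about 12. If urns ran within site, the cost is instead a rejection rate of 3.1 to 4.3% where 5% was available. This is a modest, inexpensive improvement, most useful for the hypotheses of no difference, where small shifts are hardest to dismiss. Confidence is medium, because the site split, the site effect and the urn procedure are all unknown.

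**What to change.** 1. State in Section 2.3 whether urns were run separately by site.
2. In Section 2.6, use Cochran-Mantel-Haenszel tests stratified by site for the binary Phase 1 outcomes.
3. Add site as a covariate to the zero-inflated Poisson models. This is two parameters if it enters both parts; if the fit is unstable at 67 participants, keep it in the count part only.
4. Name a site-adjusted comparison for Phase 1 attendance and for completion of the cannabis modules.
5. Report enrolment by arm and site, and show SIM uptake of tobacco modules and NRT by site descriptively. A site covariate alone would not show whether uptake came from one clinic.

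The cost is one or two extra parameters per count model at n = 67, some SAP wording and a few lines of SAS. The clinic each participant attended should already be on record, so no new data should be needed.

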2.4 Measures

2.4.1 Substance Use. At intake, the Substance Use Disorders section of the SCID (First et al., 1995) was administered to determine SUD diagnoses. The timeline follow-back (TLFB) procedure (Sobell and Sobell, 1992) was used to obtain self-reported substance use information for the 90 days preceding intake, and then again at each clinic visit to assess substance use since the last clinic visit. TLFB assessments included cannabis, cigarettes, other tobacco and nicotine products (including smokeless tobacco and electronic cigarettes), alcohol, other drug use, and NRT use. Nicotine dependence was assessed at baseline using the Fagerstrom Test of Nicotine Dependence (FTND; Heatherton et al., 1991).

Cannabis abstinence was verified via twice-weekly observed collection of urine specimens which were then tested immediately thereafter. Cannabis and adulterant testing were performed using dipstick tests with a minimum THC detection cutoff of 50 ng/ml (<http://www.americanscreeningcorp.com>). Failure to submit a specimen without an excused absence was treated as a cannabis-positive result.

Self-reported tobacco abstinence was verified using expired carbon monoxide (CO; coVita Micro + Smokerlyzer: <http://covita.net/micro+.html>). Participants with a CO level ≤ 5 were considered tobacco abstinent. In the event of self-reported tobacco abstinence, a breath CO > 5 , and self-reported cannabis use (which could increase CO level), tobacco abstinence was verified using urine cotinine (ONSCREEN Cotinine Test; <http://www.americanscreeningcorp.com>).

2.5 Outcomes. Primary engagement outcomes included Phase 1 treatment retention defined as clinic attendance, and treatment engagement defined by completion of cannabis and tobacco computer modules, and initiation and duration of NRT. The primary cannabis outcome was the duration of continuous abstinence achieved during Phase 1, assessed using the twice-weekly observed urine specimens. Primary tobacco outcomes included the percent of participants who

made at least one self-reported tobacco quit attempt during Phase 1, and percent of participants who achieved sustained tobacco abstinence over the final eight weeks of Phase 1. Secondary outcomes included: percent of participants who achieved any biologically-verified cannabis or tobacco abstinence (≥ 1 negative urine THC/cotinine specimen or expired carbon monoxide < 5 ppm), percent of participants who achieved cannabis abstinence throughout the final four weeks of treatment, reduction in percent days of cannabis and tobacco use during treatment relative to baseline, and point-prevalence cannabis and tobacco abstinence at the 12-week follow-up assessment.

2.6 Data Analysis. Sociodemographic and baseline drug use characteristics between treatment conditions were compared using t-tests for continuous measures and chi-square tests for nominal measures (Table 1). The primary cannabis and tobacco abstinence outcomes were analyzed using an intent-to-treat approach with missing biological verification data and dropouts treated as a positive indicator of cannabis or tobacco use. Longest duration of continuous abstinence from cannabis (primary), number of days abstinent from tobacco, and number of tobacco quit attempts (primary) were all zero-inflated and therefore could not be analyzed with models that assume continuous, normally distributed outcomes. We therefore analyzed each of these outcomes using a zero-inflated Poisson model which provides an odds ratio describing the relative likelihood of achieving a zero-response to the outcome in the two treatment arms and a ratio of means describing the relative mean of the outcome in the two treatment groups. Additionally, several binary outcomes were analyzed via chi-square tests: cannabis abstinence in the final 4 weeks, point prevalence abstinence at the end of treatment, achievement of at least 50% reduction in days of using cannabis from intake to the final 4 weeks, and achievement of continuous tobacco abstinence for ≥ 2 consecutive weeks. Phase 2 outcomes were analyzed using descriptive statistics. Statistical comparisons were not made between SEQ Phase 2 and SIM Phase 1 outcomes because of the lack of Phase 2 data due to only a 30% participation rate for SEQ during Phase 2. All analyses were performed using SAS version 9.4.

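### The cotinine check on a raised CO depends on admitted cannabis use, so a tobacco abstainer who denies cannabis but is THC-positive has no route to verified abstinence

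*Combined protocol and SAP*

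**What the plan says.** Section 2.4.1 gives two routes to verified tobacco abstinence.

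- **CO alone:** "Participants with a CO level ≤ 5 were considered tobacco abstinent".
- **Cotinine:** "In the event of self-reported tobacco abstinence, a breath CO > 5 , and self-reported cannabis use". The test is done on urine, and the reason given is that cannabis can push the CO reading up.

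No rule is written for CO > 5 when cannabis use is denied.

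The same section handles cannabis status differently: "Cannabis abstinence was verified via twice-weekly observed collection of urine specimens which were then tested immediately thereafter", using "dipstick tests with a minimum THC detection cutoff of 50 ng/ml". Self-reported use comes from the timeline follow-back (TLFB), taken at intake and "then again at each clinic visit to assess substance use since the last clinic visit". Section 2.2.1 sets the Phase 1 schedule: "Participants attended the clinic twice weekly, where they received nine MET/CBT computer modules". Urine was given at those visits.

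Section 2.5 makes "percent of participants who achieved sustained tobacco abstinence over the final eight weeks of Phase 1" a primary tobacco outcome, next to a self-reported quit attempt. Section 2.6 counts missing biological verification as use and adds a binary outcome of at least two consecutive weeks of tobacco abstinence.

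**The concern.** The plan's reason for the cotinine step is that cannabis use can raise CO. That reason applies whether or not the participant admits the use. Section 2.4.1 does not accept self-report as proof of cannabis abstinence and requires an observed urine. Yet self-report alone decides whether a raised CO is checked further, although in Phase 1 a THC result should be at hand.

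Sustained abstinence over eight weeks is at stake, because one visit scored as tobacco use can end it. Some true tobacco abstainers who still use cannabis would be lost, and the outcome would depend partly on candour about cannabis. If hypothesis 2 is right and the simultaneous (SIM) arm has more true abstainers, an equal per-visit loss in both arms would shrink the absolute difference from the sequential (SEQ) arm.

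**Working it through.** The documents give no sample size calculation, power or frequency for this case, so there is no figure of the plan's to reproduce. The check is a trace of the rule, followed by an illustration of size.

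**Rule trace, for a participant who reports tobacco abstinence (2.4.1 and 2.6)**

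| CO | Cannabis self-report | THC dipstick | Result |
|---|---|---|---|
| ≤ 5 | either | either | abstinent |
| > 5 | use reported | either | cotinine decides |
| > 5 | denied | negative | no cotinine, not verified |
| > 5 | denied | positive | no cotinine, not verified |

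In the third row nothing points to cannabis as the source of the CO, so the plan's reason for cotinine does not arise. In the fourth row it does arise, but the route is closed. Whether that visit is read as a failed CO or as missing verification under 2.6, it counts as tobacco use.

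**Loss of sustained eight-week abstinence**

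Inputs:
- eight weeks (2.5);
- clinic visits twice weekly (2.2.1);
- the CO schedule is not stated, so both 8 readings (weekly) and 16 readings (2 × 8) are shown;
- q, the chance per reading that a true abstainer falls in the fourth row, is an assumption;
- independence between readings is an assumption.

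If one such reading breaks the outcome, P(lost) = 1 − (1 − q)^k.

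| q | k = 8 | k = 16 |
|---|---|---|
| 1% | 1 − 0.99^8 = 7.7% | 1 − 0.99^16 = 14.9% |
| 2% | 1 − 0.98^8 = 14.9% | 1 − 0.98^16 = 27.6% |
| 5% | 1 − 0.95^8 = 33.7% | 1 − 0.95^16 = 56.0% |

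**Clustering.** 1 − (1 − q)^k is concave in q, so for the same average q the loss falls when the chance varies between people. At the extreme, a share q of abstainers fall in the fourth row at every reading and the rest never do. The loss is then q itself: 1%, 2% or 5%.

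**The two-week outcome.** This is any run of at least two weeks, not a fixed window. With twice-weekly CO a run is four clean visits.
- Someone abstinent for exactly four visits is lost with probability 1 − (1 − q)^4 = 3.9%, 7.8% and 18.5% at q = 1%, 2% and 5%.
- Over eight abstinent visits, a clean run starts at visit 1 with probability (1 − q)^4, or first starts right after a failed visit at one of visits 2 to 5, each with probability q(1 − q)^4. So P(lost) = 1 − (1 − q)^4(1 + 4q) = 0.1%, 0.4% and 2.3%.

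**Weight of one participant.** With 67 enrolled (2.1) and arms assumed about equal, one misclassified participant moves an arm's rate by 1/33.5, about 3 percentage points.

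**The case against.** The case may be rare. It needs a true tobacco abstainer who still uses cannabis, has CO > 5 and denies the use. A reader might infer that denial is to be expected from people in cannabis treatment, but the documents do not support this. Incentives under 2.2.1 followed the urine result, so denial earned nothing, and no rate of denial is given. This stands, and it is why the size can only be shown as a range.

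The rule is the same in both arms and errs in the same direction as the missing-as-use convention in 2.6. That also stands. A reader might infer a bias in favour of one arm, but nothing in the documents shows that the case was more frequent in either.

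The scoring is inferred, since no sentence says that CO > 5 with cannabis denied counts as smoking. But both available readings give that score, and no other route to abstinence is written.

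A positive dipstick can reflect older use, so it is a poor replacement for self-report. This is a reason to add it as an alternative trigger; it is not a reason to leave it out.

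Finally, enrolment ended in September 2016 and the document is dated August 2018, so rewording alone may change nothing for the data already collected. That limits what can be done about past visits, but it does not close the gap in the rule.

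**Conclusion.** The gap is real but narrow. On the text of 2.4.1 and 2.6, a participant who reports no tobacco, has CO > 5, denies cannabis and is THC-positive cannot be verified as abstinent and is counted as using tobacco.

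For a true sustained abstainer, the chance of losing the primary eight-week outcome is 8% to 34% with weekly CO, or 15% to 56% with twice-weekly CO, for assumed q from 1% to 5% and independent readings. With full clustering it falls to q itself. None of these q values comes from the documents, and a CO reading at the same visit as the urine is itself an inference.

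A reader might infer that every tobacco outcome is damaged. The documents do not support that. The quit-attempt outcome is self-reported and unaffected. The two-week outcome is at material risk only for someone whose abstinence barely reaches two weeks. Nor can it be said that any result of this trial was changed, because the number of such visits is not reported.

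**What to change.** **Wording of 2.4.1.** Trigger cotinine when tobacco abstinence is reported, CO is above 5, and either cannabis use is self-reported or the THC dipstick at that visit is positive. Run cotinine on the same urine.

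**NRT users.** No rule for them is written in the cotinine step. If the test also detects nicotine from NRT (an assumption to confirm), abstainers on NRT would still fail. In Phase 1 the clinic supplied NRT only to SIM, so the wider trigger would mainly rescue participants not on NRT and could act unequally between arms. Flag cotinine results at visits with TLFB-reported NRT use as uninformative; in practice this means the positives, since a negative still supports abstinence. Report the tobacco abstinence comparison with and without the rescued visits, by arm.

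**If specimens are no longer available.** From the recorded CO, TLFB and THC data, count by arm the visits with reported tobacco abstinence, CO > 5, cannabis denied and THC-positive urine. State how they were scored, and run a sensitivity analysis that rescores them as abstinent.

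**Cost.** One phrase, one NRT rule and a few extra cotinine strips, with no added visit or specimen. Some tests will only confirm smoking, because a THC-positive result can reflect older use. The retrospective version costs one tabulation and one rerun of the tobacco analysis.
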